3.5 TREATMENT ADHERENCE RATE AND EXTENT OF EXPOSURE

Treatment adherence refers to a subject's adherence to the daily dosing schedule as assessed by the number of tablets of samidorphan or placebo dispensed, returned and lost. Treatment

adherence of samidorphan or placebo will be calculated as a percentage for the treatment periods as follows:

$$\text{Adherence} = 100 \times \frac{(\text{Total Tablets Dispensed} - \text{Total Tablets Returned} - \text{Total Tables Lost})}{\text{Total Tablets Scheduled to be Taken}}$$

Treatment adherence of samidorphan/placebo will be summarized for Part A using the Safety Population and for Part B using the Safety population for Part B.

Exposure to study drug will be summarized separately for olanzapine and samidorphan/placebo. It will be summarized for Part A using Safety Population and for Part B using the Safety Population for Part B. The exposure is defined as follows.

$$\text{Exposure (days)} = \text{Date of last dose of study drug} - \text{date of first dose of study drug} + 1$$

In addition, the time-weighted average olanzapine dose level will be summarized for Part A placebo-controlled period and Part B ALKS 3831 treatment period using the FAS 1 population. Average olanzapine dose level in a treatment period is defined as follows.

$$\text{Average olanzapine dose level} = \frac{\text{Sum(olanzapine dose level * days on such dose level)}}{\text{exposure}}$$

3.6 EFFICACY ANALYSIS

3.6.1 Change in PANSS total Score

The primary endpoint is the change in PANSS total score from randomization to Day 92 and will be evaluated by treatment group (ALKS 3831 pooled vs. the placebo group [olanzapine alone]) using a 2-sided mixed-model for repeated measures (MMRM) to test for equivalence at an alpha level of 0.05. The primary analysis will be conducted in the FAS 1 population.

The null hypothesis is that the PANSS total score change from randomization to Day 92 of ALKS 3831 treatment group will be different to that of the placebo group [olanzapine alone]. The bound of the 2-sided 95% CIs of the difference between the changes of ALKS 3831 – Placebo [olanzapine alone] will be outside the equivalence interval of -10 and 10.

If this analysis shows equivalence, similar analyses on individual dose levels will be performed.

Change in PANSS total score from baseline to Day 92 will be analyzed using MMRM model. The MMRM model will include variables for weight change strata in the olanzapine lead-in period, treatment group, visit, and treatment group-by-visit interaction term as categorical fixed effect, baseline value will be included as a covariate. An AR(1) covariance structure will be

applied for the MMRM. The Kenward-Roger approximation [2] will be used to adjust the denominator degree of freedom. The analysis will be performed on all observed post-randomization scores without imputation of missing data.

A sample of SAS implementation code for analyzing change from randomization to Day 92 using an MMRM is given below.

```
proc mixed data=datain;  
class strata usubjid trt visit;  
  model change = strata trt visit trt*visit base  
    / DDFM=KENWARDROGER;  
repeated visit/ type=AR(1) subject=usubjid;  
lsmeans trt*visit / diff cl;  
run;
```

The least squares (LS) mean, standard error (SE), and LS mean difference between pooled ALKS 3831 treatment group and placebo [olanzapine alone], as well as between each ALKS 3831 treatment group and the placebo [olanzapine alone] at Day 92, along with the 95% CI, will be summarized.

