2 SAMPLE SIZE CONSIDERATIONS

Sample size calculations are based on the primary endpoint of absolute change in PANSS total score. These calculations assume an equivalence margin of 10 points, a standard deviation of 20 points, and a true difference of 0 points. With these assumptions, 280 randomized subjects provide 95% power to demonstrate equivalence on the primary endpoint (absolute PANSS total score change from randomization to the end of Part A) with a 2-sided test at an alpha level of 0.05. These 280 subjects represent 70 subjects for each treatment arm (ALKS 3831 5 mg, ALKS 3831 10 mg, ALKS 3831 20 mg, and placebo) in a 1:1:1:1 ratio. For the primary analysis, subjects in the 3 ALKS 3831 treatment groups will be pooled for comparison with placebo. If this analysis shows equivalence, follow-up analyses on individual dose levels will be performed. Assuming a 20% discontinuation rate prior to randomization, an estimated 350 subjects will be enrolled in this study.

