3.6.1.1 Sensitivity Analysis

ANCOVA (analysis of covariance) model will be conducted with the olanzapine lead-in period weight change strata and treatment group as factor and the baseline weight as the covariate for FAS 1. The ANCOVA model will be based on the LOCF (last observation carried forward) imputation, that is, if a subject misses a post-baseline scheduled visit, a record for the scheduled visit will be imputed using the value from the most recent post-baseline visit.

For both FAS 1 and FAS 2 populations, summary of change from baseline in PANSS total score and subscales at each visit will also be presented using descriptive statistics. Change from Part B baseline will also be summarized at each visit in Part B.

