3.6.2 Percent Change in Body Weight

The secondary endpoint, percent change in weight from randomization to Day 92, will be evaluated by treatment group using an MMRM approach similar to that of the primary endpoint. Pooled and individual ALKS 3831 treatment group will be compared to the placebo [olanzapine alone] group with a 2-sided hypothesis test to test for superiority at an alpha level of 0.05. The secondary efficacy analysis will be conducted in both FAS 1 and FAS 2 population. The MMRM model includes variables for the weight change strata in olanzapine lead-in period, treatment group, visit, and treatment group-by-visit interaction term as categorical fixed effect; baseline weight value will be included as a covariate.

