3.11.1.1 Scheduled analysis visit

Scheduled analysis visits are visits upon scheduled time points as specified in the protocol (Table 1 Schedule of Visits and Assessments).

Scheduled analysis visits during the study period will be the same as the nominal visits collected in eCRF. There would be one valid value of assessment kept for each scheduled analysis visit in summary/analysis statistics.

The scheduled repeat measurements at the same visit will be handled as described in SAP Section 3.1.

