3.11.1.3 Early termination (ET) visit

An early termination (ET) visit can be mapped to a scheduled visit and be used for analysis and summaries only if there is no valid value already at the mapped visit.

A mapped ET visit will be treated as a scheduled visit to be included in table summaries. Otherwise, it will be treated as an unscheduled visit.

Two rules will be used to map an ET visit.

First, a 7-day (inclusive) window (\leq last dose date + 7) will be used to determine if the assessment at the ET visit is considered to be an on-treatment result. If an ET visit is within 7 days after the last dose of samidorphan/placebo, it will be considered as a valid on-treatment

visit.

Second, visit windows (inpatient stay is excluded) will be applied to determine to which visit an ET valid on-treatment assessment can be mapped to. Visit windows are defined in Table 8 below.

If a subject didn't complete the Part A, his/her ET assessment will not be mapped to Part B visits, i.e. Visit 14 to 23.

Table 8: Visit Window Definition

Analysis Visit to be Mapped to	Target Study Day	Visit Window
Visit 6	15	[9, 18]
Visit 7	22	[19, 25]
Visit 8	29	[26, 32]
Visit 9	36	[33, 43]
Visit 10	50	[44, 57]
Visit 11	64	[58, 71]
Visit 12	78	[72, 85]
Visit 13	92	[86, 98]
Visit 16	99	[99, 102]
Visit 17	106	[103, 109]
Visit 18	113	[110, 116]
Visit 19	120	[117, 127]
Visit 20	134	[128, 141]
Visit 21	148	[142, 155]
Visit 22	162	[156, 169]
Visit 23	176	[170, 183]

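### The primary PANSS model forces one common variance on all visits, so the Day 92 standard error that decides equivalence is wrong if Day 92 variance differs from the across-visit average

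*SAP*

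**What the plan says.** SAP 3.6.1 fixes the covariance structure for the primary endpoint twice: in the text ("An AR(1) covariance structure will be" applied) and in the sample code ("repeated visit/ type=AR(1) subject=usubjid"). In PROC MIXED this is the homogeneous form, with one variance for all visits and one correlation parameter. Kenward-Roger degrees of freedom are specified, and observed scores are analysed without imputation.

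The decision rule is built on one visit. "The bound of the 2-sided 95% CIs of the difference between the changes of ALKS 3831" minus placebo is compared with -10 and 10 at Day 92. Protocol Table 1 schedules post-baseline PANSS in Part A at Visits 6, 7, 9, 11 and 13 (Days 15, 22, 36, 64 and 92).

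On variability, SAP 2 offers a single figure: "These calculations assume an equivalence margin of 10 points, a standard deviation of 20 points". Neither document gives an SD by visit.

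The only other inferential PANSS model, in SAP 3.6.1.1, is an LOCF ANCOVA. The same section also plans that a "summary of change from baseline in PANSS total score and subscales at each visit will also be presented using descriptive statistics".

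For percent weight change, SAP 3.6.2 says the endpoint "will be evaluated by treatment group using an MMRM approach similar to that of the primary endpoint". It lists fixed effects and a covariate but no covariance structure.

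**The concern.** Homogeneous AR(1) estimates one pooled variance. The Day 92 standard error is then driven largely by four earlier visits, although only Day 92 enters the decision. If scores are more spread at Day 92 than on average, the interval is too narrow and equivalence is declared too easily. If they are less spread, the interval is too wide and power is lost. Kenward-Roger adjusts inference within the chosen structure; it cannot supply a Day 92 variance that the structure does not contain.

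Weight raises a related question. If AR(1) were carried over, a change over 1 day (Day 8 to Day 9) and one over 84 days (Day 8 to Day 92) would share one variance, because "Scheduled analysis visits during the study period will be the same as the nominal visits collected in eCRF" and weight is measured at every visit.

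**Working it through.** **Inputs from the documents.** 70 per arm, three active arms pooled (210 vs 70), margin 10, SD 20, true difference 0 (SAP 2); 95% CI rule and AR(1) (SAP 3.6.1); PANSS days (protocol Table 1).

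**The plan's own figure.** SE = 20 × √(1/70 + 1/210) = 2.760, so 10/SE = 3.623.
- Two bounds at 5% each: 2Φ(3.623 − 1.645) − 1 = 95.2%, which matches the stated 95%. A single bound at 2.5%, Φ(3.623 − 1.96), also gives 95.2%.
- The 95% CI rule that SAP 3.6.1 writes down: 2Φ(3.623 − 1.96) − 1 = 90.4%. This is the baseline used below.

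**Assumptions, not in the documents.** Day 92 SD is 20 and SD is linear in days. Five correlation shapes were tried: AR(1) 0.7 and 0.8, exchangeable 0.6, and decay to 0.85 or 0.90 per 14 days. Data are complete, or have 30% monotone dropout at random, spread evenly over the four gaps.

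**Method.** Find the AR(1) parameters that best fit each assumed covariance matrix by Gaussian likelihood. Then take r = model SE / true (sandwich) SE of the Day 92 contrast. False equivalence at a true difference of 10 is Φ(−1.96 r).

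By hand for the 75% row: SDs 15.0, 15.5, 16.4, 18.2, 20.0 have root mean square 17.1, and 17.1/20 = 0.855. The fitted r is 0.86–0.87, so the fitted SD stays close to the root-mean-square SD. Φ(−1.96 × 0.865) = Φ(−1.695) = 4.5%.

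| Day 15 SD as % of Day 92 | r, complete | False equivalence | r, 30% dropout | False equivalence |
|---|---|---|---|---|
| 60% | 0.78–0.80 | 5.8–6.2% | 0.76–0.77 | 6.6–6.9% |
| 70% | 0.83–0.85 | 4.9–5.1% | 0.81–0.83 | 5.3–5.7% |
| 72% | 0.85–0.86 | 4.7–4.9% | 0.82–0.84 | 5.0–5.4% |
| 75% | 0.86–0.87 | 4.4–4.6% | 0.84–0.86 | 4.7–5.1% |
| 90% | 0.94–0.95 | 3.2% | 0.92–0.95 | 3.1–3.6% |
| 100% | 1.00 | 2.5% | 0.98–1.02 | 2.3–2.7% |
| 125% | 1.14–1.15 | 1.2–1.3% | 1.13–1.19 | 1.0–1.4% |

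A rise-and-fall profile (SDs 16, 20, 23, 22, 20; complete data) gives r = 0.97–1.00 and 2.5–2.9%.

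Power in the 125% row, complete data: 2Φ(3.623 − 1.96 × 1.145) − 1 = 2Φ(1.379) − 1 ≈ 83%, down from 90.4%.

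**Finite-sample check.** REML fits with strata, baseline, treatment, visit and interaction, 2,000 simulated trials (Monte Carlo error about 0.3–0.5 points). At 75% with complete data, false equivalence was 4.9% under AR(1) and 2.5% under unstructured. With constant variance it was 2.8% and 2.5%. The unstructured fits started from the true matrix and omitted the Kenward-Roger inflation, which favours them somewhat.

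**Weight, illustration only.** Suppose AR(1) is carried over and the SD of percent change grows from 0.8–2.0 at Day 9 to 3.1–4.5 at Day 92. SE ratios of about 0.58 to 0.84 then follow. Φ(−1.96 × 0.58) ≈ 13% and Φ(−1.96 × 0.84) ≈ 5%, against 2.5% in the favourable direction.

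**The case against.** **No by-visit SDs are given, so harm is not shown.** This stands as a limit on size and direction. A reader might infer that the plan inflates false equivalence; the documents do not support that. Constant SDs cause no error, a rise-and-fall profile very little, and falling SDs make the test conservative. Early spread could even be raised, since protocol 8.1.1 lets the taper from prior antipsychotics run to Day 15. What remains is that equal variances are built in, with no stated basis, where the decision is made.

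**The stated alpha is 0.05, so 2.5% is a strict benchmark.** Partly right. The 2.5% per bound comes from the 95% CI rule, and the planned 95% power reproduces at 5% per bound. Measured against 5%, an excess needs a steep rise: a Day 15 SD below about 70% of Day 92 with complete data, or below about 72–75% with the assumed dropout. But SAP 3.6.1 specifies a 95% interval, and one whose SE is about 14% too small does not have 95% coverage.

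**Other analyses cover it.** The by-visit summaries would reveal unequal SDs, but only once results are in hand. The LOCF ANCOVA avoids AR(1), but it also changes the handling of missing data and, as written, adjusts PANSS for baseline weight. It cannot isolate a covariance error.

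**AR(1) is not specified for weight.** Correct. A reader might infer it from the word *similar*; the text does not say it. SAP 3.6.2.1 also plans an LOCF ANCOVA and a mixed model with visit in days, neither of which uses the AR(1) MMRM. The documented gap for weight is an unnamed structure.

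**Conclusion.** The point holds conditionally and should be fixed before unblinding. SAP 3.6.1 makes the primary interval depend on equal variances at five visits, with no alternative, fallback or robust standard error. If Day 92 variance differs from the across-visit average, the Day 92 SE is wrong by roughly the ratio of the root-mean-square SD to the Day 92 SD.

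Under rising SDs with complete data, false equivalence per bound is about 3.2%, 4.5% and 6% when the Day 15 SD is 90%, 75% and 60% of Day 92. Under falling SDs the cost is power. Every figure other than the SE of 2.760 and the baseline powers rests on assumed SD profiles, correlations and dropout.

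For weight, the conclusion is only that the structure must be stated. The 5–13% range needs both an assumed AR(1) and assumed SDs, and should not be read as the trial's error rate.

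**What to change.** Before unblinding:

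1. In SAP 3.6.1, replace `type=AR(1)` with `type=UN` over the five scheduled PANSS visits (5 × 6/2 = 15 parameters, about 280 subjects), keeping Kenward-Roger.
2. State an ordered fallback for non-convergence: heterogeneous Toeplitz, then ARH(1). For the structured fallback, use empirical (sandwich) SEs with between-within degrees of freedom.
3. Settle early-termination values. SAP 3.11.1.3 says "An early termination (ET) visit can be mapped to a scheduled visit and be used for analysis and summaries", and its Table 8 is not endpoint-specific. A PANSS score could land on Visit 8, 10 or 12, where none is scheduled. That could give 8 levels and 36 parameters. Nine covariances would have no data, because an early-termination value is a subject's last (5 pairs with later visits from Visit 8, 3 from Visit 10, 1 from Visit 12). State that such a value creates no new level, and name the scheduled PANSS visit that receives it.
4. In SAP 3.6.2 and 3.6.3, state that weight follows the same rule and not homogeneous AR(1). The fallback is likeliest to be needed here (10 post-baseline visits, 55 parameters), in FAS 2 and in subgroups.

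**Cost.** A few SAP sentences, a small code change and a fallback list to maintain. In the REML check with constant variance, the mean 95% half-width was 5.45 under unstructured and 5.43 under AR(1) with complete data (0.4% wider), and 6.22 against 6.28 with 30% dropout. With a Day 15 SD at 75% it was 5.45 against 4.68 (16% wider), which is the correction itself. Convergence in small subgroups was not tested.

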5. INTRODUCTION

5.1. Background

Olanzapine is regarded as one of the most effective antipsychotics with well-recognized efficacy and other advantages such as decreased incidence of extrapyramidal symptoms. However, it also has safety and tolerability limitations which have been demonstrated to affect compliance and retention of patients on olanzapine therapy [Lieberman, 2005]. In particular, results of the CATIE (Clinical Antipsychotic Trials of Intervention Effectiveness) study identify olanzapine as an effective atypical antipsychotic agent associated with the highest weight gain (4.2 kg over up to 18 months of treatment and an overall >7% body weight in 30% of subjects) and a comparatively higher discontinuation rate due to increases in body weight and metabolic effects than other antipsychotic agents [Lieberman, 2005]. Further, it is estimated that between 40-60% of people with schizophrenia abuse alcohol and/or illicit drugs [Lubman, 2010], and these “dual diagnosis” patients have worse outcomes on a variety of measures [Batki, 2009; Dixon 1999].

ALKS 3831 is a combination drug under investigation for treatment of schizophrenia. The principle active component in ALKS 3831 is olanzapine. The other active component is samidorphan, a new chemical entity that clinical studies have shown to limit the weight gain caused by olanzapine alone. This effect was first seen in a proof-of-concept study conducted in healthy adults (Study ALK33-301). This effect appears to be specific to antipsychotic weight gain because samidorphan did not cause meaningful changes in weight when administered as a single agent in adults with binge eating disorder (Study ALK33-101).

As stated previously, despite being regarded as one of the most effective antipsychotics for the treatment of schizophrenia, safety and tolerability limitations have affected compliance and retention of patients on olanzapine therapy. As a result, many patients are switched from olanzapine to other antipsychotics to address tolerability issues even if the alternative antipsychotic is regarded as less effective. The presence of samidorphan in ALKS 3831 is to enhance the benefit and decrease the risk of the principal ingredient, olanzapine.

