3.6.6 Change in Clinical Global Impression - Severity

The CGI-S is a 7-point scale ranging from 1=normal to 7=extremely ill. .

The change from baseline to Day 92 in CGI-S will be carried out using the MMRM model including the weight change strata in olanzapine lead-in period, treatment group, visit, and a treatment group-by-visit interaction term as categorical fixed effects; baseline CGI-S value will be included as a covariate.

A summary of CGI-S at each visit will be presented using descriptive statistics for Part A and Part B.

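### The MMRMs give baseline and lead-in weight stratum one effect shared by all visits; this can bias the Day 92 difference, but only if those effects change over time and related dropout differs by arm

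*SAP*

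**What the plan says.** For the primary endpoint, the SAP 3.6.1 text lists "weight change strata in the olanzapine lead-in period, treatment group, visit, and treatment group-by-visit interaction term as categorical fixed effect", with the baseline value as a covariate. The sample code agrees: "model change = strata trt visit trt*visit base". Neither contains a baseline-by-visit or stratum-by-visit term. The covariance is AR(1), and on missing data the SAP says: "The analysis will be performed on all observed post-randomization scores without imputation of missing data". The reported result is the Day 92 difference.

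The same form recurs elsewhere:

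- SAP 3.6.2 (percent weight change) also crosses only treatment with visit, and "baseline weight value will be included as a covariate". SAP 3.6.3 extends this to absolute weight change.
- SAP 3.6.6 (CGI-S): "baseline CGI-S value will be included as a covariate", again without a visit interaction.
- SAP 3.6.7 (waist circumference) uses the same structure.

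The supporting analyses differ by endpoint. The LOCF ANCOVA for weight (SAP 3.6.2.1) adjusts for stratum and baseline weight at the endpoint itself. The LOCF ANCOVA for PANSS (SAP 3.6.1.1) lists baseline weight, not baseline PANSS, as its covariate.

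**The concern.** A single coefficient is right only if the covariate acts equally on change at every visit. There are two reasons to doubt that.

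- **Baseline PANSS.** At equal variances, the slope of a change score on baseline is the correlation with baseline minus 1. It steepens as that correlation decays over the weeks.
- **Lead-in stratum and weight.** Weight is first measured after baseline on Day 9, one day after the Day 8 baseline, when the strata can hardly differ in change. Stratifying on lead-in gain presumes that they differ later.

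The documents give no reason why lead-in weight stratum should affect PANSS at all.

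Where an effect grows over time, the shared coefficient is too small at Day 92. An MMRM on observed data relies on a correct mean model at each visit for its missing-at-random validity. A covariate can therefore be in the model and still be under-corrected at the visit that matters. The results at stake are the PANSS equivalence interval and the weight comparison.

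**Working it through.** **1. The plan's own figure.** SAP section 2 gives a margin of 10, SD 20, true difference 0, and 70 placebo against 3 × 70 = 210 pooled subjects.

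- SE = 20 × √(1/70 + 1/210) = 2.760.
- Power = 2Φ(10/SE − z) − 1.
- z = 1.645 (a 90% interval) gives 95.2%, which matches the stated 95%.
- z = 1.96 (the 95% interval in SAP 3.6.1) gives 90.4%. That mismatch is a separate matter; 90.4% is the reference value below.

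**2. Where bias can come from.** Let b₉₂ be the true covariate slope at Day 92 and b the shared fitted slope. An uncorrected part (b₉₂ − b) × x remains at Day 92. Roughly, it enters the treatment difference as (b₉₂ − b) times the between-arm difference in mean x among subjects still observed. The first factor is zero if the effect is constant over visits. The second is about zero, by randomization, if dropout depends on x equally in both arms. Bias needs both factors.

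**3. Simulated bias.** 70 against 210 subjects, REML with AR(1). Assumptions that are not in the documents:

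- PANSS: baseline SD 10; slope moving from −0.10 at Day 15 to −0.50 at Day 92; correlation parameter 0.8; about 30% dropout.
- Weight: stratum effects rising from about 0 to +1 and +3 percentage points at Day 92 (strong case +2 and +6); true difference −1.5; about 30% dropout.

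Bias of the Day 92 difference under the SAP model:

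| Dropout pattern | PANSS, points | Weight, percentage points |
|---|---|---|
| None | −0.05 | 0.00 |
| Related to covariate, same in both arms | −0.06 | 0.00 (strong +0.01) |
| Related in placebo only | −0.76 | +0.19 (strong +0.40) |
| Opposite directions by arm | −1.52 | +0.38 |

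Monte Carlo SE is about 0.1 for PANSS and 0.02 to 0.03 for weight. With both interactions added, no bias exceeded 0.03 in absolute value for either endpoint.

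A second set of PANSS runs (400 runs, odds ratio 2 per SD of baseline, dropout after Day 36) gave the shift between the SAP model and the interaction model:

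- same in both arms: 0.00
- placebo only: −0.55
- opposite by arm: −1.14

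Relative size: 0.55/10 to 1.52/10 is about 5 to 15% of the PANSS margin; 0.19/1.5 to 0.40/1.5 is about 13 to 26% of the assumed weight effect. In the opposite-by-arm PANSS case, coverage was 92.3% and equivalence power 0.753, against 95.1% and 0.787 with the interactions.

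**4. Precision at the planned SD.** The empirical SE for PANSS went from 2.748 to 2.722 without dropout and from 3.092 to 3.061 with equal 30% dropout. That is about 1% of the SE, or 2% of the variance. The second set of runs gave a complete-data variance ratio of 1.01. With variance ratio k, power is 2Φ(10√k/2.760 − 1.96) − 1: 90.7% at k = 1.01 and 91.1% at k = 1.02, against 90.4%.

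**5. Parameters added.** PANSS has 5 post-baseline visits in Part A (Days 15, 22, 36, 64, 92): 4 for baseline and 2 × 4 = 8 for three strata, in all 12. Weight has 10 (Days 9, 10, 15, 22, 29, 36, 50, 64, 78, 92): 9 + 2 × 9 = 27.

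**The case against.** The best case for the plan is that nothing in the documents shows the harmful pattern. They give no post-randomization dropout rate and no link between dropout and baseline PANSS or lead-in stratum. Protocol 5.1 does cite for olanzapine "a comparatively higher discontinuation rate due to increases in body weight and metabolic effects than other antipsychotic agents", but every arm here takes olanzapine, and the statement says nothing about a one-week lead-in stratum predicting dropout differently by arm. Dropout driven by weight measured after randomization is partly carried by the repeated measures themselves. For weight there are also partial checks: the LOCF ANCOVA and further mixed models in SAP 3.6.2.1, and the analysis within each lead-in stratum in SAP 3.6.5.

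Most of this stands, and it rules out two stronger readings:

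- A reader might infer that any dropout related to these covariates biases the Day 92 difference. It does not: with the same dependence in both arms, no bias was detectable.
- A reader might infer a real gain in power, to 92 or 93%. That needs a variance reduction of 5 to 8%, which arises when the SD of change is close to the baseline SD. It does not carry over to the planned SD of 20 with a baseline SD of 10.

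The objection does not remove the point. Protocol 5.3 itself expects attenuated weight gain to improve retention, so weight-related dropout concentrated on placebo is a plausible pattern, though still a hypothesis. The MMRM with continuous lead-in weight change in SAP 3.6.2.1 lists no covariate-by-visit term either. PANSS has no comparable check, because no listed adjusted analysis gives baseline PANSS an effect specific to Day 92.

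**Conclusion.** The specification is weaker than it need be, and the consequence is conditional. If baseline or stratum effects change over visits, adjustment at Day 92 is incomplete. If, in addition, covariate-related dropout differs by arm, the Day 92 difference is biased: by about 0.5 to 1.5 PANSS points and about 0.2 to 0.4 percentage points of weight in the cases tried. If either condition fails, no bias is expected.

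The direction follows the assumed dropout pattern. For weight, losing high lead-in gainers mainly from placebo understates the benefit. For PANSS, the documents predict no direction. The sizes depend on the assumed slopes, stratum effects and dropout of about 30%. The change should be judged as protection against bias, since the gain in precision is negligible. Severity: minor.

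**What to change.** Before the Part A data are unblinded, add `base*visit` and `strata*visit` to the model statement in SAP 3.6.1, and the matching terms to the text. Make the same change in SAP 3.6.2, 3.6.3, 3.6.6 and the waist model in 3.6.7. Keep the Day 92 treatment contrast as the reported result.

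The cost is one line of text and code per model, no new data, and 12 extra parameters for PANSS or 27 for weight with 280 subjects. If the effects are in fact constant over visits, the loss is negligible.
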